3.8. Analysis Windows

3.8.1. Definitions

Study Day 1 is defined as the day when the first dose of study drug was taken. The first dose date is defined as the earliest nonmissing start date of B/F/TAF study drug recorded on the Study Drug Administration eCRF.

Study Days are calculated relative to Study Day 1. For events that occur on or after the Study Day 1 date, study days are calculated as (visit date minus date of the first dose plus 1). For events that occur prior to Study Day 1, study days are calculated as (visit date minus date of the first dose).

Last Dose Date is defined as the maximum, nonmissing end date of B/F/TAF recorded on the Study Drug Administration eCRF form with “Study Drug Permanently Discontinued” box checked for subjects who prematurely discontinued study drug or completed study drug according to the Study Drug Completion eCRF.

If the date of last dose is missing (eg, due to lost to follow-up), the maximum of nonmissing study drug start dates and end dates, the clinical visit dates, and the laboratory visit dates excluding the date of 30-day follow-up visit will be used to impute the last dose date.

Last Study Date is the maximum of nonmissing study drug start dates and end dates, the clinic visit dates, and the laboratory visit dates, including the 30-day follow-up visit date.

Baseline value is defined as the last nonmissing value obtained on or prior to the Study Day 1 for all assessments.

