6.2. Analysis of the Efficacy Endpoints

6.2.1. US FDA-Defined Snapshot Algorithm

The analysis window at Week 96 is defined as from Study Day 631 to Study Day 714, inclusive. All HIV-1 RNA data collected on-treatment (ie, data collected up to 1 day after the last dose date of study drug) will be used in the US FDA-defined snapshot algorithm. Virologic outcome for Week 96 will be defined using the following categories:

- **HIV-1 RNA < 50 copies/mL:** this includes subjects who have the last available on-treatment HIV-1 RNA < 50 copies/mL in the analysis window
- HIV-1 RNA \geq 50 copies/mL: this includes subjects
 - 1) Who have the last available on-treatment HIV-1 RNA \geq 50 copies/mL in the analysis window, or

- 2) Who do not have on-treatment HIV-1 RNA data in the analysis window and
 - a) Who discontinue study drug prior to or in the analysis window due to lack of efficacy, or
 - b) Who discontinue study drug prior to or in the analysis window due to AE or death and have the last available on-treatment HIV-1 RNA ≥ 50 copies/mL, or
 - c) Who discontinue study drug prior to or in the analysis window due to reasons other than AE, death, or lack of efficacy and have the last available on-treatment HIV-1 RNA ≥ 50 copies/mL
- **No Virologic Data in Window:** this includes subjects who do not have on-treatment HIV-1 RNA data in the analysis window because of the following:
 - 1) Discontinuation of study drug prior to or in the analysis window due to AE or death and the last available on-treatment HIV-1 RNA < 50 copies/mL, or
 - 2) Discontinuation of study drug prior to or in the analysis window due to reasons other than AE, death, or lack of efficacy and the last available on-treatment HIV-1 RNA is < 50 copies/mL, or
 - 3) Missing data during the window but on study drug

The flowchart of the snapshot algorithm is provided in [Appendix 2](#).

The number and percentage of subjects with HIV-1 RNA < 50 copies/mL, HIV-1 RNA ≥ 50 copies/mL, and reasons for no virologic data at Week 96 will be summarized using the Full Analysis Set. The 95% confidence intervals (CIs) for percentages of subjects with HIV-1 RNA < 50 copies/mL and HIV-1 RNA ≥ 50 copies/mL will be constructed using the Exact method. The analysis will be done using the FAS. The above analysis will be repeated for Week 72.

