The analysis window at Week 72 is defined as from Study Day 463 to Study Day 546, inclusive. All HIV-1 RNA data collected on-treatment (ie, data collected up to 1 day after the last dose date of study drug) will be used in the US FDA-defined snapshot algorithm defined above.

The same analysis will be repeated for proportion of subjects with HIV-1 RNA < 20 copies/mL at Week 72 and Week 96 as defined by US FDA-defined snapshot algorithm. The visit window was defined in [Table 3-1](#).

The Week 72, and Week 96 virologic outcomes for the US FDA-defined snapshot algorithm will be listed.

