Appendix 2. Flowchart of US FDA-defined Snapshot Algorithm (for Switch Trial)

The following flowchart for US FDA-defined snapshot algorithm is based on the US FDA Guidance on Human Immunodeficiency Virus-1 Infection: Developing Antiretroviral Drugs for treatment {U. S. Department of Health and Human Services 2015}.

* On-Treatment HIV-1 RNA data include all HIV-1 RNA data for subjects who are on-going and HIV-1 RNA data up to 1 day after the last dose date of study drug for subjects who prematurely discontinue or complete study drug.

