Last Dose Date in ADSL was defined in Section [3.8.1](#).

For subjects with a partial last dosing date of B/F/TAF (ie, month and year of last dose are known), the minimum of (death date, if available), (the latest of the dispensing dates of B/F/TAF bottles, B/F/TAF start dates and end dates (based on EX dataset), and the imputed last dose date [day imputed as 15])} will be used as the final imputed last dose date. However if dispensing date’s month is after last dose date’s month, data query is needed.

Last Study Date is the latest of the study drug start dates and end dates, the clinic visit dates, and the laboratory visit dates, including the 30-day follow-up visit date, for subjects who prematurely discontinued study or who completed study according to the Study Completion eCRF. If study drug start dates or end dates is partially missing (ie, only year and month are known), the day will be imputed as 15 for the purpose of this analysis. If the subject died and the death date is complete (ie, not partial date) and before the imputed last study date, the complete death date should be used as the imputed last study date.

9. Toxicity Grades:

- 1) For toxicity grade summaries, include all postbaseline graded results up to 30 days after the last dose of B/F/TAF, not just those used in by-visit summaries.
- 2) For glucose grading, as specified in SAP Section 7.2.2.1, the treatment-emergent flag cannot be determined for nonfasting glucose (including glucose results without a known fasting status). As a result, these records will be excluded from the “Maximum Treatment-emergent Toxicity Grade” summary in the “Treatment-emergent Laboratory Abnormalities” or “Treatment-emergent Grade 3 or 4 Laboratory Abnormalities” summary tables. In addition, fasting glucose and non-fasting glucose will be listed as two separate laboratory tests in the “Laboratory Abnormalities” and “Grade 3 or 4 Laboratory Abnormalities” listings. Only a maximum postbaseline toxicity flag will be displayed and the treatment-emergent flag will not be displayed for nonfasting glucose as the treatment-emergent flag cannot be determined for nonfasting glucose.

10. Graded Laboratory Abnormalities Summary

The following labels will be used for treatment-emergent laboratory abnormalities and treatment-emergent Grade 3 or 4 laboratory abnormalities summary tables and listings:

Battery	Lab Test Label Used in l-labtox Listing	Toxicity Direction	Lab Test Label Used in t-labtox Table

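### A last dose known only to the month is imputed without visit dates, so a completer's on-drug Week 96 HIV-1 RNA can be discarded as off-treatment

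*SAP*

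**What the plan says.** Three SAP rules meet here.

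- **Partial date, Appendix 7 item 8.** With month and year known, the last dose is "the latest of the dispensing dates of B/F/TAF bottles, B/F/TAF start dates and end dates (based on EX dataset" and a third candidate, "the imputed last dose date [day imputed as 15". The latest of these is taken and limited by the death date if there is one. Visit and sample dates are not candidates.
- **Wholly missing date, Section 3.8.1.** The maximum is taken over drug start and end dates and also "the clinical visit dates, and the laboratory visit dates excluding the date of 30-day follow-up visit will be used to impute the last dose date".
- **On-treatment cut-off, Section 6.2.1.** The snapshot uses "data collected up to 1 day after the last dose date of study drug". Appendix 2 confirms that completers are included: the limit is "up to 1 day after the last dose date of study drug for subjects who prematurely discontinue or complete study drug".

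SAP 1.2 (Study Duration) says that all subjects leave the study at Week 96. Protocol 6.3.1 lists dispensing and accountability at every treatment visit. Protocol 6.4.1 asks subjects who stop drug early to keep attending visits through Week 96. SAP Appendix 1, footnote d, places the ESDD visit within 72 hours of the last dose.

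**The concern.** Less information about the date gives the better classification. A completer who attends Week 96 late in the month, with the day of the last dose unrecorded, can be assigned the 15th. The sample from that visit then counts as off-treatment. Had the month also been unrecorded, the visit date would have been imputed and the sample kept.

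On-treatment status decides the snapshot category, so a measured value below 50 copies/mL becomes absent data for a reason unrelated to virology. A completer's value of 50 or more could vanish in the same way. The on-treatment CD4 summaries in SAP 6.2.2 use the same one-day cut-off.

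There is also an error in the other direction. A subject who stopped on the 2nd and was sampled off drug on the 12th counts as on treatment, because only death can pull the imputed date below the 15th.

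**Working it through.** The plan has no figure to reproduce: the sample size rests on feasibility (SAP 1.3). The check applies the rules as written.

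**Windows.** For Week 96, "The analysis window at Week 96 is defined as from Study Day 631 to Study Day 714, inclusive". This agrees with the midpoint rule: (588 + 672)/2 + 1 = 631 and 672 + 42 = 714. The window has 714 − 631 + 1 = 84 days and visits are 12 weeks (84 days) apart, so it normally holds one scheduled sample. For Week 72, (420 + 504)/2 + 1 = 463 and 504 + 42 = 546, also as stated.

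**Rules.**
- Item 8: last dose = min(death, max(dispensing dates, drug start/end dates, 15th)).
- Section 3.8.1: last dose = max(drug dates, clinic and laboratory visit dates without the 30-day follow-up).
- A sample is kept if its date ≤ last dose + 1 day.

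**Illustration.** The last dose is known only as June 2020, with no death, and no dispensing or drug date after the 15th:

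| Week 96 draw | Last dose, item 8 | Kept? | Last dose, 3.8.1 | Kept? |
|---|---|---|---|---|
| 15 June | 15 June | yes | 15 June | yes |
| 16 June | 15 June | yes | 16 June | yes |
| 17 June | 15 June | no | 17 June | yes |
| 22 June | 15 June | no | 22 June | yes |
| 30 June | 15 June | no | 30 June | yes |

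If a bottle is dispensed on the day of the draw, item 8 gives the draw date and all five samples are kept. That is the usual Week 72 case. A subject who stays on drug beyond that month has a last dose in a later month, so the Week 72 sample is safe in any event.

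**Share of days at risk.** Days after the 16th number 15 in a 31-day month, 14 in a 30-day month and 13 in February 2020: 7 × 15 + 4 × 14 + 13 = 174 of 366, or 47.5%. Over 2018 to 2020 the share is 47.4%.

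**Value of one subject.** Appendix 7 item 1 shows 86 in the Safety Analysis Set and leaves the Full Analysis Set blank. Taking 86 as its upper bound, 1/86 = 1.16 points. With the SAP's exact method, starting for illustration from full suppression:

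| Suppressed | Proportion | 95% CI |
|---|---|---|
| 86/86 | 100% | 95.8 to 100 |
| 85/86 | 98.8% | 93.7 to 100.0 |
| 84/86 | 97.7% | 91.9 to 99.7 |
| 83/86 | 96.5% | 90.1 to 99.3 |

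**Expected loss.** The number of completers with a partial date is not in the documents. Assume 0 to 3, with final draws spread evenly over the month of the last dose. The expected loss is then 0 to 3 × 0.474 × 1.16 = 1.65 points.

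**The case against.** The best defence is that leaving visit dates out is deliberate and sensible. Subjects who stop drug are asked to keep attending, so a rule that takes any visit date can count off-drug samples as on-treatment. Section 3.8.1 has that weakness and is not a clean benchmark. This stands, and it limits the fix. It does not justify ignoring the Week 96 visit of a subject recorded as having completed study drug.

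The stakes are modest, which also stands. The primary Week 24 analysis is done and will not be repeated (SAP 6.1.1). Weeks 72 and 96 are secondary and descriptive. Reasons for no virologic data are tabulated, individual outcomes are listed, and missing-as-failure and missing-excluded results are shown, so an affected subject could be noticed. Protocol 9.1.5 requires drug start and end dates in the source, and 9.1.6 provides for data queries, so partial dates should be rare.

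A reader might infer more than the documents support:

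- *That the last dose is always set to the 15th.* It is not; a later dispensing or drug date overrides it.
- *That Week 72 is equally exposed.* It is affected only for a subject who stops at about that visit, is sampled after the 16th of the same month, and has no later dispensing or drug date.
- *That nothing is dispensed at Week 96.* This is an inference from SAP 1.2. The combined dispensing and accountability row in SAP Appendix 1 still marks Week 96.
- *That every failure could be hidden.* A subject with no on-treatment value in the window is still classed as 50 or more if drug was stopped for lack of efficacy, or if drug was stopped early and the last on-treatment value was 50 or more.

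**Conclusion.** The point holds for Week 96 completers whose last dose is known only to month and year. Item 8, joined to the one-day cut-off, can discard a sample taken on drug, and it conflicts with what 3.8.1 would do with less information.

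Each suppressed subject lost costs about 1.2 points of Week 96 success. This assumes a Full Analysis Set of 86, no other on-treatment HIV-1 RNA in the window, and no dispensing or drug date after the 15th. About 47% of calendar days put a draw at risk. The total effect cannot be stated, because the number of partial dates is unknown and may be zero; the 0 to 1.65 points above is a range under assumption, not an estimate. The bias has no fixed direction, since values of 50 or more can be dropped and off-drug values can be admitted. It is worth repairing because the repair is small and uses dates already collected.

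**What to change.** In Appendix 7 item 8:

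1. For subjects recorded as study-drug completers on the Study Drug Completion eCRF, add the Week 96 visit date, if it falls in the known month, to the dates from which the latest is taken. The draws on the 17th, 22nd and 30th above would then be kept.
2. For premature discontinuers, cap the imputed date at the ESDD visit date as well as the death date. Add no other visit dates, because these subjects may attend off drug. In the example of a stop on the 2nd, an ESDD visit by the 5th moves the cut-off to the 6th and excludes the sample of the 12th.
3. If any partial date changes a Week 72 or Week 96 snapshot category, also show that result with the day set to the first and to the last possible day of the month. This covers the rare Week 72 case, which step 1 does not reach.

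The cost is a sentence or two in the SAP and a small change to the ADSL derivation. SAP Section 1 provides for documenting changes made after finalization in the clinical study report. The cap does not remove every off-drug sample: if the ESDD visit is itself held late, on the 12th in that example, the sample still counts. If there are no partial dates, nothing changes.

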7.2.2.1. Treatment Emergent Laboratory Abnormalities

Treatment-emergent laboratory abnormalities are defined as values that increase at least 1 toxicity grade from baseline at any postbaseline time point, up to 30 days from the last dose date of B/F/TAF. If the relevant baseline laboratory value is missing, any abnormality of at least Grade 1 observed within the time frame specified above will be considered treatment-emergent.

Fasting glucose and nonfasting glucose (including glucose results without a known fasting status) are graded based on different grading scales as specified in the protocol.

Treatment-emergent laboratory abnormalities will be summarized for fasting glucose. Maximum postbaseline grade, instead of treatment-emergent grade, for nonfasting glucose (including glucose results without a known fasting status) will be summarized, as nonfasting glucose was not assessed at baseline visit for most of the subjects; therefore, an abnormality is treatment-emergent or not cannot be determined for these subjects.

Both urine RBC based on microscopic examination, labeled as Hematuria (Quantitative), and urine blood based on a dipstick, labeled as Hematuria (Dipstick), are assessed and assigned a toxicity grade in this study. Hematuria (Quantitative) is a reflex test. Urine RBC based on microscopic examination or Dipstick will be presented in laboratory toxicity summary tables and listings.

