7.2.2.2. Summaries of Laboratory Abnormalities

The following summaries (number and percentage of subjects) for treatment-emergent laboratory abnormalities will be provided by lab test; subjects will be categorized according to the most severe postbaseline abnormality grade for a given lab test:

- Treatment-emergent laboratory abnormalities
- Treatment-emergent Grade 3 and 4 laboratory abnormalities
- Treatment-emergent Grade 2, 3, and 4 laboratory abnormalities

For all summaries of laboratory abnormalities, the denominator is the number of subjects with any nonmissing postbaseline values up to 30 days after the last dose date of B/F/TAF.

A by-subject listing of all treatment-emergent laboratory abnormalities and treatment-emergent Grade 3 or 4 laboratory abnormalities will be provided by subject ID number and visit in chronological order.

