Note: Prothrombin Intl. Normalized Ratio (INR) and Prothrombin Time (PT) were graded based on the protocol defined toxicity grade scale. The results and toxicity grade will be listed in listing, but not be summarized in lab toxicity summary table. Due to the reflexive nature of the quantitative urine RBC test, results will be combined with the dipstick test of urine blood as described below. General rule is that urine RBC (Quantitative) should always be used first (if available), no matter if it is collected at the same time of Urine Blood (Dipstick) or not. The combined Urine RBC (hematuria, Quantitative or Dipstick) toxicity grade will be used for “Maximum treatment emergent toxicity grade” summary.

Is Post-BL Urine RBC (Quant.) Result Available?	Is BL Urine RBC (Quant.) Result Available?	Is Post-BL Urine Blood (Dipstick) Result Available?	Is BL Urine Blood (Dipstick) Result Available?	How to Determine Treatment-Emergent Toxicity for “Urine RBC (Hematuria, Quantitative or Dipstick)”
Yes	Yes			Compare post BL Urine RBC (Quant.) toxicity grade to BL Urine RBC (Quant.) toxicity grade. If post BL toxicity is greater than BL toxicity, then treatment emergent
Yes	No			Treatment emergent. Use post BL Urine RBC (Quant.) toxicity grade
No		Yes	Yes	Compare posy BL Urine Blood (Dipstick) toxicity grade to BL Urine Blood (Dipstick) toxicity grade. If post BL toxicity grade is greater than BL toxicity, then treatment emergent
No		Yes	No	Treatment emergent. Use post BL Urine Blood (Dipstick) toxicity grade
No		No		Do not count subject in the denominator for “Urine RBC (Hematuria, Quantitative or Dipstick)”

11. Renal related laboratory evaluation

- 1) Unit conversion for renal safety tests derived from related tests with conventional units
 - a) Urine RBP (ug/L) to creatinine (mg/dL) ratio: $1 \text{ (ug/L)} / \text{(mg/dL)} \times 100 \text{ x ug/g}$
 - b) Urine Beta-2-microglobulin (mg/L) to creatinine (mg/dL) ratio: $1 \text{ (mg/L)} / \text{(mg/dL)} \times 10^5 \text{ ug/g}$
 - c) UP (mg/L) to creatinine (mg/dL) ratio: $1 \text{ (mg/dL)} / \text{(mg/dL)} \times 1000 \text{ x mg/g}$

Calculation of ratios:

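### The hematuria rule drops every postbaseline dipstick grade once a subject has any postbaseline quantitative RBC, so the summarised maximum grade can be too low

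*SAP*

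**What the plan says.** SAP 7.2.2.1 grades hematuria by dipstick and by microscopy, and notes that "Hematuria (Quantitative) is a reflex test". Treatment-emergent abnormalities are "values that increase at least 1 toxicity grade from baseline at any postbaseline time point". The next sentence adds that, where the relevant baseline value is missing, any result of Grade 1 or higher counts as treatment-emergent.

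SAP 7.2.2.2 then states that "subjects will be categorized according to the most severe postbaseline abnormality grade for a given lab test". Appendix 7 item 9 tells the programmer that toxicity-grade summaries are to "include all postbaseline graded results up to 30 days after the last dose of B/F/TAF, not just those used in by-visit summaries".

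Appendix 7 item 10 gives the hematuria rule: "urine RBC (Quantitative) should always be used first (if available), no matter if it is collected at the same time of Urine Blood (Dipstick". "The combined Urine RBC (hematuria, Quantitative or Dipstick) toxicity grade will be used for" the summary of maximum treatment-emergent grade. The decision table has five rows:

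1. Postbaseline RBC and baseline RBC both present: compare the two RBC grades.
2. Postbaseline RBC present, baseline RBC absent: "Treatment emergent. Use post BL Urine RBC (Quant.) toxicity grade".
3. No postbaseline RBC, but dipstick present at both times: compare the dipstick grades.
4. No postbaseline RBC, postbaseline dipstick present, no baseline dipstick: treatment-emergent at the dipstick grade.
5. Neither postbaseline result: "Do not count subject in the denominator for" the combined test.

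In rows 1 and 2 both dipstick cells are blank. The label table in the same item keeps Urine Blood (the dipstick) as its own test in the listing but gives it no label in the summary table.

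**The concern.** Because RBC is a reflex test, a subject can have it at some visits and not at others. The rule chooses the method once for the subject, not sample by sample. A single postbaseline RBC is enough to set aside dipstick grades from visits where no RBC was done, and those grades have no other row in the summary tables. The general rules for the same tables ask for the most severe grade over all postbaseline graded results.

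At stake is one of the three urinalysis lines in the treatment-emergent tables of a single-arm study. An affected subject could drop out of the Grade 2 to 4 and Grade 3 and 4 tables.

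A lesser matter is row 2, which never looks at the baseline dipstick and does not repeat the Grade 1 minimum of SAP 7.2.2.1.

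**Working it through.** There is no planned figure to reproduce, so the check applies the table to worked patterns. These are hypothetical, not trial data.

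**Inputs**
- Grades, from the urinalysis section of Protocol Appendix 4: dipstick 1+ is Grade 1, 2+ is Grade 2, 3+ to 4+ is Grade 3. For males, 6–10 RBC/HPF is Grade 1, above 10 to 75 is Grade 2, above 75 is Grade 3. There is no Grade 4.
- Urinalysis is scheduled at every visit (Protocol 6.10), so a baseline dipstick would normally exist.
- The Safety Analysis Set is 86 (mock disposition table, SAP Appendix 7 item 1).

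**1. Unit of the rule.** The SAP does not name it outright. Two features point to the subject: RBC takes precedence whether or not it comes from the same collection, and the last row removes a subject from the denominator.

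**2. Main example.** Male, baseline dipstick negative, no baseline RBC.

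| Sample | Dipstick | RBC |
|---|---|---|
| Week 12 | 3+ (Grade 3) | none |
| Week 48 | any | 7/HPF (Grade 1) |

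- Rule as written: a postbaseline RBC exists and baseline RBC does not, so row 2 applies. Result: treatment-emergent Grade 1.
- Same table applied to each sample, then the maximum: Week 12 falls in row 3 (Grade 3 against baseline Grade 0) and gives Grade 3; Week 48 gives Grade 1. Result: Grade 3.

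The subject is still counted as having treatment-emergent hematuria, but two grades too low.

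**3. Is the pattern isolated?** Let each result be Grade 0, 1, 2, 3 or missing (5 values) for RBC and dipstick, at baseline and two postbaseline visits: 25 × 25 × 25 = 15,625 patterns. The subject-level rule gives a lower grade than visit-by-visit application in 1,250 of them. The gap needs exactly one visit with RBC, which gives 2 (which visit) × 5 (the ignored dipstick at that visit) × 125 (grade combinations in which the dipstick-only visit gives the higher treatment-emergent grade) = 1,250. This shows that the error is possible; it is not an expected frequency.

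**4. When does it vanish?** Suppose RBC is present if and only if the dipstick on that sample is positive. Each sample then has 1 + 3 × 4 = 13 admissible patterns, and 13 × 13 × 13 = 2,197 in all. None shows a lower grade, because a visit without RBC always has a Grade 0 dipstick. The documents do not state this trigger.

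**5. Size per subject.** 1/86 = 1.2 percentage points. The number affected is not given; if it were 0, 1, 2 or 5 (an assumption), the shift would be 0, 1.2, 2.3 or 5.8 points. The denominator is subjects with a postbaseline value, so it may be slightly below 86.

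**6. Row 2.** With baseline dipstick 2+ (Grade 2), no baseline RBC and a postbaseline RBC of 12/HPF (Grade 2), row 2 reports treatment-emergent Grade 2. Against the baseline dipstick there is no increase. Literally applied, row 2 would also call a Grade 0 RBC treatment-emergent.

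**The case against.** The strongest reply is that the rule is a deliberate, disclosed refinement. Item 10 explains that the results are combined because microscopy is reflexive, and preferring it to a dipstick is sensible. SAP 7.2.2.2 speaks of the most severe grade for a given test, and item 10 defines that test. Item 9 is aimed at not restricting summaries to by-visit records. The preference for RBC on the same sample stands and is not questioned. It does not justify discarding a dipstick from a different sample, where there is no RBC to prefer. The combined test is named as quantitative or dipstick, and dipstick results are graded, so the most severe grade of that test should include them.

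A second reply is that the reflex fills the gap: no RBC means a negative dipstick. Rows 3 and 4 tell against relying on this. Under a perfect reflex, a subject with no postbaseline RBC could have only Grade 0 dipsticks, and row 3 could never find an increase. The table itself provides for a positive dipstick without RBC. Protocol Appendix 4 also notes that laboratories other than the one it names grade only the dipstick, although that scale is generic and does not show that other laboratories were used here.

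A third reply is that the table could be applied record by record, which would remove the understatement. That is possible, and the SAP should then say so.

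Two stronger readings are not supported:

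- A reader might infer that row 2 contradicts the treatment-emergent definition. The missing-baseline sentence in SAP 7.2.2.1 covers it if the relevant baseline is RBC, and the row errs toward over-reporting.
- A reader might infer that the rule hides a true Grade 3. The dipstick keeps its own place in the listing, and the documents do not say that a dipstick 3+ outranks microscopy.

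**Conclusion.** The point holds in limited form. On the subject-level reading, which the wording favours, a postbaseline RBC from one visit removes dipstick grades from other visits, and the summarised maximum can be lower than SAP 7.2.2.2 and Appendix 7 item 9 require. The loss is two grades in the main example. An RBC at baseline only does not trigger it; the table then falls back to the dipstick.

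Row 2 is a secondary matter. It is a conservative application of the missing-baseline rule, but it ignores baseline information that is normally available and omits the Grade 1 minimum.

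The impact may be nil. It depends on how often a positive dipstick has no RBC, which the documents do not give. Each affected subject moves a percentage by about 1.2 points in one descriptive safety row. No endpoint or test depends on it. This is a low-priority correction.

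**What to change.** Replace the subject-level choice in Appendix 7 item 10 with a sample-level one:

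- For each postbaseline sample, take the RBC grade if that sample has one, otherwise its dipstick grade.
- Take the maximum over all postbaseline samples up to 30 days after the last dose.
- Form the baseline in the same way: RBC grade if present, otherwise the baseline dipstick grade. Count a result as treatment-emergent when the postbaseline grade exceeds it.
- If both baseline results are missing, count a result as treatment-emergent only at Grade 1 or higher, as in SAP 7.2.2.1. Row 4 needs the same condition.

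If record-by-record use was always intended, one sentence naming the unit settles the main point.

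The cost is one programming rule on the same data, with the change recorded in the study report as SAP Section 1 requires. The downside is small: some comparisons will set an RBC grade against a dipstick grade, which a footnote can disclose.
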